4.2.2.2. Secondary Outcomes Reflecting Conditions or Symptoms Associated with Pain and/or Opioid Use

The effects of the interventions on several conditions or symptoms often associated with pain and/or opioid use will be evaluated through ascertainment of a set of patient-reported outcomes using validated instruments (see **Table 4.3**).

Table 4.3. Secondary Outcomes Reflecting Conditions or Symptoms Associated with Pain and/or Opioid Use

Domain	Instrument or Data Source	Time-Points for Assessment
Depression	Patient Health Questionnaire (PHQ)-9	Weeks 0, 12, 24, 36
Anxiety	Generalized Anxiety Disorder (GAD)-7	Weeks 0, 12, 24, 36
Sleep quality	PROMIS Sleep Disturbance 6a + Sleep Duration Question	Weeks 0, 12, 24, 36
Fatigue	PROMIS Fatigue SF 6a	Weeks 0, 12, 24, 36
Other symptoms	Dialysis Symptom Index	Weeks 0, 12, 24, 36
Physical functioning	PROMIS Physical Functioning SF 6b	Weeks 0, 12, 24, 36
Quality of life	Single-Item QOL Scale [SIS] from McGill Quality of Life (MQOL)	Weeks 0, 12, 24, 36
Coping	Coping Strategies Questionnaire: 1-item version	Weeks 0, 12, 24, 36
Self-efficacy	PROMIS Self-Efficacy for Managing Chronic Conditions – Managing Symptoms – Short Form 8A + single item targeting self-efficacy for pain	Weeks 0, 12, 24, 36
Discrimination	Everyday Discrimination Scale	Weeks 0, 36
Satisfaction with treatment	Patient Global Impression of Change	Weeks 0, 12, 24, 36
Family intrusion	PROMIS Satisfaction with Social Roles and Activities	Weeks 0, 12, 24, 36
Social support	Multidimensional Scale of Perceived Social Support (MSPSS)	Weeks 0, 12, 24, 36

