7.2. Baseline Data Collection and PRO Ascertainment – (within 4 weeks of Screening)

Baseline data includes demographic information, medical history via checklist, dialysis history, substance use history, pain history, prescribed and over-the-counter medications, and use of behavioral or other non-pharmacologic interventions for pain.

PRO questionnaires will be administered by telephone by a centralized CATI team (see **Section 4.2.3**). The order of preference for the day of the week for completing CATI, from optimal to the least preferred, is as follows:

1. The day following the first dialysis treatment of the week: Tuesday for patients on a Monday-Wednesday-Friday schedule, or Wednesday for patients on a Tuesday-Thursday- Saturday schedule, or Monday for patients on a Sunday-Tuesday-Thursday schedule. The first dialysis treatment of the week is defined as the treatment following the 72-hour dialytic interval.
2. The day following the second dialysis treatment of the week: Thursday for patients on a Monday-Wednesday-Friday schedule, or Friday for patients on a Tuesday-Thursday-Saturday schedule, or Wednesday for patients on a Sunday-Tuesday-Thursday schedule.
3. Preferably, within the first hour of the 2nd dialysis session of the week which is Wednesday for patients on a Monday-Wednesday-Friday schedule, or Thursday for patients on a Tuesday-Thursday-Saturday schedule, or Tuesday for patients on a Sunday-Tuesday-Thursday schedule.

To the extent possible, the timing with respect to dialysis will be kept consistent throughout the duration of the trial.

If all attempts to complete a follow up CATI call are unsuccessful, the Clinical Center Principal Investigator may authorize the site study coordinator to complete the PROs using paper forms chairside during dialysis. This approach is expected to be used only under exceptional circumstances.

The baseline PRO questionnaires include*:

- Brief Pain Inventory 7-item Interference (BPI-Interference)
- Brief Pain Inventory 4-item Severity (BPI-Severity)
- Pain Catastrophizing Scale (PCS) SF6
- Opioid Use Timeline Follow-Back (TLFB)
- Pain Mapping Questionnaire
- Single Item Quality of Life Scale [SIS] from the McGill Quality of Life (MQOL) Questionnaire
- Patient Health Questionnaire (PHQ-9)
- Generalized Anxiety Disorder (GAD-7)
- Coping Strategies Questionnaire 24 (CSQ-24)
- Single item targeting self-efficacy for pain

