7.4.3. Follow-Up PROs (Week 12)

Follow-up PRO questionnaires will be administered by telephone by a centralized CATI team. To the extent possible, the surveys should be performed using the same timing with respect to dialysis as was used for the Baseline PROs. The Week 12 PRO ascertainment will provide the data for the primary outcome.

The follow-up PRO questionnaires performed at Week 12:

- Brief Pain Inventory 7-item Interference (BPI-Interference) – primary outcome
- Brief Pain Inventory 4-item Severity (BPI-Severity)
- Pain Catastrophizing Scale (PCS) SF6
- Opioid Use Timeline Follow-Back (TLFB)
- Single Item Quality of Life Scale [SIS] from the McGill Quality of Life (MQOL) Questionnaire
- Patient Health Questionnaire (PHQ-9)
- Generalized Anxiety Disorder (GAD-7)
- Coping Strategies Questionnaire (CSQ) 1-item
- Single item targeting self-efficacy for pain
- PROMIS Self-Efficacy for Managing Chronic Conditions – Managing Symptoms – Short Form 8A
- PROMIS Sleep Disturbance 6a + Sleep duration
- PROMIS-Fatigue SF 6a
- PROMIS Physical Functioning SF 6b
- Multidimensional Scale of Perceived Social Support (MSPSS)
- Dialysis Symptom Index

- Patient Global Impression of Change (PGIC)
- PROMIS Satisfaction with Social Roles and Activities

7.4.4. End of Phase 1 Intervention, Week 24 PROs, and Determination of Eligibility for Buprenorphine (Week 24)

Follow-up PRO questionnaires will be administered by telephone by a centralized CATI team. To the extent possible, the surveys should be performed using the same timing with respect to dialysis as was used for the Baseline PROs.

The follow-up PRO questionnaires performed at Week 24 include:

- Brief Pain Inventory 7-item Interference (BPI-Interference)
- Brief Pain Inventory 4-item Severity (BPI-Severity)
- Pain Catastrophizing Scale (PCS) SF6
- Opioid Use Timeline Follow-Back (TLFB)
- Single Item Quality of Life Scale [SIS] from the McGill Quality of Life (MQOL) Questionnaire
- Patient Health Questionnaire (PHQ-9)
- Generalized Anxiety Disorder (GAD-7)
- Coping Strategies Questionnaire (CSQ) 1-item
- Single item targeting self-efficacy for pain
- PROMIS Self-Efficacy for Managing Chronic Conditions – Managing Symptoms – Short Form 8A
- PROMIS Sleep Disturbance 6a + Sleep duration
- PROMIS-Fatigue SF 6a
- PROMIS Physical Functioning SF 6b
- Multidimensional Scale of Perceived Social Support (MSPSS)
- Dialysis Symptom Index
- Patient Global Impression of Change (PGIC)

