10.2.2.1. Analyses of the Primary Endpoint for the Phase 1 Randomization

Question 1 (Table 10.1): Does a PCST intervention consisting of weekly, live, coach-led sessions improve outcomes at 12 weeks?

Question 1 addresses the primary trial hypothesis. The primary efficacy endpoint, the change in BPI Interference between baseline and 12 weeks, and will be analyzed using a linear mixed effects model.⁶² The linear mixed effects model will include fixed effects of intervention, time, and interactions between intervention and time, taking into account the repeated measures over time and clustering of recruitment sites via random effects. All repeated measures of the BPI Interference scores at baseline and 12 weeks will be included in the model as the dependent variable. The linear mixed effects model is expressed as

$$y_{ijk} = \beta_0 + \beta_1 X_{ij} + \beta_2 I(T_{ijk} = 12) + \beta_3 X_{ij} I(T_{ijk} = 12) + \gamma^T \mathbf{W}_{ij} + \theta_i + \alpha_{ij} + \varepsilon_{ijk},$$

where y_{ijk} is the BPI Interference score for participant ij ($i = 1, 2, \dots, 14$; $j = 1, 2, \dots, n_i$; n_i is number of participants from recruitment site i) at time point k ($k = 1, 2$), X_{ij} is the binary intervention indicator ($X_{ij} = 1$ if PCST; $X_{ij} = 0$ if Usual Care) for participant ij , T_{ijk} is the study weeks for participant ij at time point k ($T_{ij1} = 0$ and $T_{ij2} = 12$), $I(\cdot)$ is an indicator function returning 1 (0) if the event is true (false), \mathbf{W}_{ij} is a vector of baseline measures, including the stratification factors, for participant ij , β 's and γ are regression parameters for the fixed effects, θ_i and α_{ij} are the regression parameters for the random effects for recruitment site i and participant ij , respectively, and ε_{ijk} is the random error for participant ij at time point k . Model diagnostics will be conducted to examine the assumption of normality. If there are potential violation of the assumptions, transformations of the data beginning with a log transformation will be explored. The primary efficacy estimand is the contrast of PCST and Usual Care for the change at the 12-week time point; i.e., β_3 . Differences in changes, their 95% confidence intervals, and p-values will be presented.

Question 2 (Table 10.1): Does a PCST intervention consisting of weekly, live, coach-led sessions for 12 weeks followed by IVR for 12 weeks improve outcomes at 24 weeks?

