10.2.3.2 Analyses of the Secondary Endpoints

The secondary endpoints include pain severity, pain catastrophizing, opioid use, other PROs, hospitalizations, falls and mortality.

For continuous endpoints, such as pain severity, pain catastrophizing, and opioid use expressed as MME/day., similar methods as described for the primary outcome will be used to compare differences in changes of the endpoints between PCST and Usual Care at 12 (**Table 10.1; Question 1**), 24 (**Table 10.1; Question 2**), and 36 (**Table 10.1; Question 3**) weeks; i.e., linear mixed effects models with adjustment for baseline measures (and additional adjustment for buprenorphine eligibility and initiation of buprenorphine for **Question 3 in Table 10.1**), taking into account the repeated measures over time and clustering of recruitment sites via random effects.

For binary endpoints, such as the composite of pain interference and opioid use, generalized linear mixed effects models with a binomial distribution and a log link adjusting for baseline measures (additionally adjusting for buprenorphine eligibility and initiation of buprenorphine for **Question 3 in Table 10.1**), taking into account the repeated measures over time and clustering of recruitment sites via random effects, will be used to compare relative risks between PCST and Usual Care at 12 (**Table 10.1; Question 1**), 24 (**Table 10.1; Question 2**), and 36 (**Table 10.1; Question 3**) weeks.

For recurrent endpoints (counts) such as number of hospitalizations and falls, participants will be followed from baseline to 36 weeks, loss-to-follow-up, or death, whichever comes first. Generalized linear mixed effects models with a Poisson distribution, an offset of follow-up time and a log link adjusting for baseline measures (additionally adjusting for buprenorphine eligibility and initiation of buprenorphine for **Question 3 in Table 10.1**) will be used to compare event rates between PCST and Usual Care during the Phase 1 study period (**Table 10.1; Questions 1 – 3**). Repeated measures over time and clustering of recruitment sites will be taken into account via random effects.

For time to event endpoints such as mortality, participants will be followed from baseline to 36 weeks, loss-to-follow-up, or death, whichever comes first. Cox proportional hazards models will be used to compare risks of

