14.2. PRO Questionnaire Schedule and Activities During Research Team Contacts

Baseline PRO Questionnaires (Week 0)

- Pain interference – Brief Pain Index (BPI) Interference⁴⁷
- Pain intensity – Brief Pain Index (BPI) Severity⁴⁷
- Pain catastrophizing – Pain Catastrophizing Scale (PCS) SF 6⁶⁷
- Opioid use – Timeline Followback⁶⁸
- Pain Mapping Questionnaire^{69, 70}
- Quality of life – Single-Item QOL Scale [SIS] from McGill Quality of Life (MQOL) questionnaire⁷¹
- Depression – Patient Health Questionnaire (PHQ-9)⁷²
- Anxiety – Generalized Anxiety Disorder (GAD-7)⁷³
- Coping – Coping Strategies Questionnaire 24 (CSQ-24)⁷⁴
- Self-efficacy - PROMIS Self-Efficacy for Managing Chronic Conditions – Managing Symptoms – Short Form 8A⁷⁵ + Single item targeting self-efficacy for pain
- Sleep quality – PROMIS Sleep Disturbance SF 6a + Sleep Duration Question^{76, 77}
- Fatigue – PROMIS Fatigue SF 6a^{76, 78}
- Physical functioning – PROMIS Physical Functioning SF 6b^{76, 79}
- Social support – Multidimensional Scale of Perceived Social Support (MSPSS)⁸⁰
- Dialysis symptom index⁸¹
- Family Intrusion – PROMIS Satisfaction with Social Roles and Activities^{76, 82}
- Discrimination – Everyday Discrimination Scale⁸³

Follow-up PRO Questionnaires Weeks 12 & 24

- Pain interference – Brief Pain Index (BPI) Interference⁴⁷
- Pain intensity – Brief Pain Index (BPI) Severity⁴⁷
- Pain catastrophizing – Pain Catastrophizing Scale (PCS) SF 6⁶⁷
- Opioid use – Timeline Followback⁶⁸
- Quality of life – Single-Item QOL Scale [SIS] from McGill Quality of Life (MQOL) questionnaire⁷¹
- Depression – Patient Health Questionnaire (PHQ-9)⁷²
- Anxiety – Generalized Anxiety Disorder (GAD-7)⁷³
- Coping – Coping Strategies Questionnaire: 1-item
- Self-efficacy - PROMIS Self-Efficacy for Managing Chronic Conditions – Managing Symptoms – Short Form 8A⁷⁵ + Single item targeting self-efficacy for pain
- Sleep quality – PROMIS Sleep Disturbance SF 6a + Sleep Duration Question^{76, 77}
- Fatigue – PROMIS Fatigue SF 6a^{76, 78}
- Physical functioning – PROMIS Physical Functioning SF 6b^{76, 79}
- Social support – Multidimensional Scale of Perceived Social Support (MSPSS)⁸⁰
- Dialysis symptom index⁸¹
- Satisfaction with treatment - Patient Global Impression of Change (PGIC)⁸⁴
- Family Intrusion – PROMIS Satisfaction with Social Roles and Activities^{76, 82}
- Internalized Stigma in Chronic Pain Scale (week 24 only)⁸⁵

Follow-up PRO Questionnaires Week 36

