- Pain interference – Brief Pain Index (BPI) Interference⁴⁷
- Pain intensity – Brief Pain Index (BPI) Severity⁴⁷
- Pain catastrophizing – Pain Catastrophizing Scale (PCS) SF 6⁶⁷
- Opioid use – Timeline Followback⁶⁸
- Quality of life – Single-Item QOL Scale [SIS] from McGill Quality of Life (MQOL) questionnaire⁷¹

- Depression – Patient Health Questionnaire (PHQ-9)⁷²
- Anxiety – Generalized Anxiety Disorder (GAD-7)⁷³
- Coping – Coping Strategies Questionnaire: 1-item
- Self-efficacy - PROMIS Self-Efficacy for Managing Chronic Conditions – Managing Symptoms – Short Form 8A⁷⁵ + Single item targeting self-efficacy for pain
- Sleep quality – PROMIS Sleep Disturbance SF 6a + Sleep Duration Question^{76, 77}
- Fatigue – PROMIS Fatigue SF 6a^{76, 78}
- Physical functioning – PROMIS Physical Functioning SF 6b^{76, 79}
- Social support – Multidimensional Scale of Perceived Social Support (MSPSS)⁸⁰
- Dialysis symptom index⁸¹
- Satisfaction with treatment - Patient Global Impression of Change (PGIC)⁸⁴
- Family Intrusion – PROMIS Satisfaction with Social Roles and Activities^{76, 82}
- Discrimination – Everyday Discrimination Scale⁸³

Research Team Contacts (Weeks 4, 8, 12, 16, 20, 24, 28, 32, and 36)

- Ascertainment of hospitalizations
- Ascertainment of falls
- Ascertainment of adverse events (SAEs and Adverse Events of Interest)
- Documentation of changes to opioid prescriber(s)
- Documentation of non-opioid analgesics, antidepressants, anxiolytic and sedatives/hypnotics
- Documentation of non-study behavioral or other non-pharmacologic treatments for pain
- Scheduling of Week 12, Week 24, and Week 36 CATI calls (as applicable)

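### The documents disagree on the baseline coping instrument (CSQ-24 or a single item), and the change-from-baseline analysis needs one scale throughout

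*Combined protocol and SAP*

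**What the plan says.** Coping is a listed secondary outcome. Table 4.3 (Section 4.2.2.2) names its instrument as "Coping Strategies Questionnaire: 1-item version" and schedules it at Weeks 0, 12, 24 and 36.

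The visit lists differ. Section 7.2 gives "Coping Strategies Questionnaire 24 (CSQ-24" at baseline. Sections 7.4.3, 7.4.4 and 7.5.4 give "Coping Strategies Questionnaire (CSQ) 1-item" at Weeks 12, 24 and 36. Appendix 14.2 follows the visit lists: "Coping – Coping Strategies Questionnaire 24 (CSQ-24" at Week 0 and "Coping – Coping Strategies Questionnaire: 1-item" afterwards. Neither baseline list has a separate one-item entry.

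On analysis, Section 10.2.3.2 does not name coping. It states that "The secondary endpoints include pain severity, pain catastrophizing, opioid use, other PROs, hospitalizations, falls and mortality", and that for continuous endpoints "similar methods as described for the primary outcome will be used to compare differences in changes of the endpoints between PCST and Usual Care". In the primary method (Section 10.2.2.1), "All repeated measures of the BPI Interference scores at baseline and 12 weeks will be included in the model as the dependent variable". Section 10.6 adds that a missing follow-up value is replaced by one from an earlier assessment, and gives baseline standing in for Week 12 as its example.

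**The concern.** A change from baseline needs the same measure at both ends. If the visit lists are right, the baseline value comes from a 24-item questionnaire and every later value from a single item. The only analysis rule that reaches coping would then stack the two as one outcome with one random intercept and one error variance.

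Coping is what the PCST intervention sets out to teach, so this secondary outcome bears directly on how the intervention works. At stake are the coping results at Weeks 12, 24 and 36. Patient Global Impression of Change has a related problem: Table 4.3 gives it a Week 0 assessment, but neither baseline list includes it, so the change model has no baseline value to use.

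**Working it through.** The plan states no figure on this point, so there is none to reproduce. The check is a comparison of the lists, followed by what the model does on each reading.

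**1. The lists side by side**

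| Source | Week 0 | Weeks 12, 24, 36 |
|---|---|---|
| Table 4.3 | one item | one item |
| Sections 7.2, 7.4.3, 7.4.4, 7.5.4 | CSQ-24 | one item |
| Appendix 14.2 | CSQ-24 | one item |

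The footnote to the schedule in Appendix 14.1 says that only the Everyday Discrimination Scale is left out at Weeks 12 and 24, and mentions no switch of coping form. It does not settle the matter: the Pain Mapping Questionnaire is also dropped after baseline without mention.

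**2. Does the change model reach coping?** By inference, yes. Coping is a secondary patient-reported outcome, such outcomes are covered as a group in Section 10.2.3.2, and no other analysis is given for it.

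**3. Between-arm contrast with complete data, on the visit-list reading.** Write μ for the mean score by arm and week. The interaction coefficient estimates

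(μ_PCST,12 − μ_PCST,0) − (μ_UC,12 − μ_UC,0).

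Baseline precedes randomization (Section 7.3), so μ_PCST,0 = μ_UC,0 in expectation and the expression reduces to μ_PCST,12 − μ_UC,12, a difference on the one-item scale. The contrast is unbiased in expectation. Each arm's own change, a one-item mean minus a CSQ-24 mean, is not interpretable.

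**4. Precision.** Set the follow-up SD to 1. Let r be the baseline SD divided by the follow-up SD, and ρ the baseline to follow-up correlation. Both are assumed, since the documents give neither. The variance of a change is proportional to 1 + r² − 2ρr, against 2(1 − ρ) on one scale. The ratio of standard errors is

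k = √[(1 + r² − 2ρr) / (2(1 − ρ))].

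- r = 2: ρ = 0.3 gives √(3.8/1.4) = 1.65; ρ = 0.7 gives √(2.2/0.6) = 1.91.
- r = 5: ρ = 0.3 gives √(23/1.4) = 4.05; ρ = 0.7 gives √(19/0.6) = 5.63.
- r = 0.5: ρ = 0.3 gives √(0.95/1.4) = 0.82; ρ = 0.7 gives √(0.55/0.6) = 0.96.

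For an effect with 90% power on one scale, power becomes Φ[(1.96 + 1.28)/k − 1.96]. That is about 50% to 40% at r = 2 and 12% to 8% at r = 5. At r = 0.5 nothing is lost. Size and direction both depend on how the two forms are scored.

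**5. Variance model.** With two time points and complete data, the standard error of the interaction still comes from within-participant differences. The mis-specification bites when values are missing, and in the 24- and 36-week models, where one error variance is pooled over visits on two scales.

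**6. Carry-forward.** Let D be the difference between the one-item follow-up mean and the CSQ-24 baseline mean with no treatment effect, and p the share of an arm with baseline carried forward. Carried-forward participants have a change of 0 and the others average D, so the arm mean is (1 − p)D. The between-arm difference is (p_UC − p_PCST)D. It is zero if dropout is equal, and grows by 0.01 × D for each percentage point of imbalance. D contains an arbitrary scale offset. At the planning attrition of 20% in Section 10.2.1, 0.20 × 640 = 128 participants could have such a value at Week 12. At later visits it arises only for those with no earlier follow-up score.

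**7. Patient Global Impression of Change.** With no Week 0 record, every Week 12 observation has the time indicator equal to 1. Only β₁ + β₃ can be estimated, not β₃, which is the planned estimand. There is also no baseline to carry forward.

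**The case against.** The strongest reply is that the documents do not establish that two scales are used. A reader might infer from Section 7.2 alone that the plan certainly mixes them. Table 4.3, which defines the outcome, puts the single item at Week 0, and it does vary visits by row (Discrimination is at Weeks 0 and 36 only). If the item is asked at baseline, or can be taken from CSQ-24, nothing is mixed. This stands, and it is why the point is a contradiction to be resolved and not a proven error. Table 4.3 is not decisive either, because its Week 0 entry for Patient Global Impression of Change matches neither baseline list.

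Second, coping reaches the change model only as one of a group of outcomes, by methods described as similar and with adjustment for baseline measures. Entering CSQ-24 as a covariate would partly fit that wording. This also stands, but the wording compares changes, and no rule tells the analyst to treat coping differently.

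Third, a reader might infer that the coping comparison between arms is meaningless or biased. Step 3 shows otherwise for complete data. The power losses in step 4 are illustrations under assumed values and not findings about this trial.

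Finally, baseline coping style is a planned effect modifier (Section 10.2.2.2), so a longer baseline form may be deliberate. That is plausible, though the plan does not say so, and it does not supply a same-scale baseline.

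**Conclusion.** The point holds as an unresolved contradiction over the baseline coping instrument, with no rule for obtaining a baseline on the follow-up scale. If the visit lists govern and the general rules are applied as written:

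- the within-arm change in coping has no meaning;
- the shared variance structure is mis-specified;
- precision may be worse, by an amount that cannot be stated without the scoring of both forms;
- carried-forward baseline values can bias the contrast, but only if dropout differs between arms.

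If the single item is available at Week 0, these problems fall away and only the visit lists need correcting.

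For Patient Global Impression of Change, the planned change estimand cannot be estimated on the collection schedule as listed.

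The reach is two secondary patient-reported outcomes. The primary endpoint, sample size and interim analysis are not affected.

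**What to change.** 1. Reconcile Table 4.3 with Section 7.2 and Appendix 14.2, and state whether a one-item coping score exists at Week 0, either asked directly or taken from CSQ-24 by a stated rule.
2. If it exists, name it as the baseline for the coping analysis. CSQ-24 can still serve the subgroup analysis.
3. If it does not, model the one-item score at Weeks 12, 24 and 36 as the outcome, with arm, visit and their interaction, and enter baseline CSQ-24 as a covariate and not as a repeated outcome. State which CSQ-24 score is used. A covariate need not share the outcome's scale.
4. In that case, exempt coping from the Section 10.6 replacement of a missing follow-up value by baseline.
5. For Patient Global Impression of Change, delete Week 0 from Table 4.3, compare follow-up scores directly between arms, and exempt it from the same replacement rule.

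The cost is wording, plus a decision on how CSQ-24 is scored. The analyses use only data that the visit lists already schedule. Under item 3 the trial cannot report a within-arm change in coping.
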